Based on recent *annual* operations, approximately 120 LVAD implantations, 60 heart transplantations, and 110 Lung transplantations were performed at Duke University Hospital during FY 2014 – 2015. This study has been individually powered to primary endpoints for each arm (Table 1) and the duration of study enrollment has been determined according to annual operations and sample-size calculations. We estimated sample size based on equivalence test of the incidence rates of a binary outcome (e.g. PGD grade 3 (PGD-3)) of two treatment groups as an illustration. Assuming the incidence rate of PGD-3 under iEPO treatment is 0.35 and acceptable margin of the equivalence is  $\pm 0.19$ , we will need 224 patients to have 80% power to detect an actual difference at 0.05 between two treatment group under this margin. This implies that the acceptable range of incidence rate for iNO treatment is from 0.21 to 0.59. Based on this estimate, we propose to enroll 200 lung transplant patients and 224 LVAD and heart transplant patients ( $n = 424$ ) over a period of 24 to 36 months; the exact time point for trial culmination between 24 and 36 months will be dependent on enrollment rate. There will be a 50% randomization rate for each inhaled agent such that 212 patients will receive iEPO and 212 patients will receive iNO.

**12. Data & Safety Monitoring:** The proposal is not introducing a new medication that has not been utilized by our group and safety has been established for this patient population through clinical practice and medication usage. Safety will, however, be determined by assessing reported, rare, adverse effects of iNO (systemic hypotension, methemoglobinemia, and rebound pulmonary hypertension after appropriate weaning) and iEPO (systemic hypotension, non-surgical bleeding related to thrombocytopenia, flushing, and rebound pulmonary hypertension after appropriate weaning) in order to accurately monitor adverse events (AE) during this study. The PI will review and sign off on AE's as they occur and perform a quarterly review and determine if AE's are related to the study or otherwise. AE's will be reported to the IRB per HRPP policies.

*Stopping Rule:* Subjects who meet the stopping criteria in section 4 continued to be enrolled and followed for primary outcome analysis. See section 4 for stopping criteria.

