**13. Privacy, Data Storage & Confidentiality:** All data collected in the case report forms (CRF) will be collected by review of the subjects routine medical record documentation or during the intraoperative portion of the study. All subjects will be given a study ID in an order to maintain their identity and subject's identity will be protected and confidentially maintained. Barcodes will be affixed to each study sample collected according to the protocol. For future review, the study number and barcode will be the only identifying information associated with the subject. All paper data will be stored in a locked cabinet in the research teams office as outlined in the research data security plan. Any computerized data will be stored within the Duke University Medical Center's Database, which is password protected, and located behind Duke Computing firewalls. Only the PI and the statisticians will have access to the data obtained from these cases.

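### No by-arm review of death, severe graft dysfunction or RV failure is planned during enrolment; safety monitoring rests on listed drug effects and case-by-case relatedness

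*Combined protocol and SAP*

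**What the plan says.** Section 12 (Data & Safety Monitoring) starts from the position that both drugs are already in local use and that their safety is established. It then sets the scope: "Safety will, however, be determined by assessing reported, rare, adverse effects of iNO" (systemic hypotension, methemoglobinemia, rebound pulmonary hypertension), with a similar list for iEPO (systemic hypotension, bleeding related to thrombocytopenia, flushing, rebound). On process, "The PI will review and sign off on AE's as they occur and perform a quarterly review"; the stated purpose of that review is to decide whether events are related to the study. Adverse events go to the IRB under institutional policy.

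The Stopping Rule paragraph of the same section reads "Subjects who meet the stopping criteria in section 4 continued to be enrolled and followed for primary outcome analysis". The section 4 criteria it points to end the study drug in one subject.

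Mortality, PGD-3, RVAD insertion and INTERMACS moderate or severe RV failure appear in Table 1 and in Measured Outcomes (section 4) as efficacy outcomes. Section 11 compares them between arms. Under Randomization and Double-Blinding, section 4 says that primary endpoint data are complete, and unblinding occurs, by ICU discharge. Section 13 adds: "Only the PI and the statisticians will have access to the data obtained from these cases". The documents describe no interim analysis, by-arm tabulation during enrolment, monitoring committee or trial-level rule.

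**The concern.** If one drug is the weaker pulmonary vasodilator, the likely harm is more graft dysfunction, more RV failure or more deaths, rather than flushing or methemoglobinemia. Each such event has a ready explanation in the operation itself. A reviewer asked whether one death or one RVAD is related to the study will usually, and reasonably, say no. Only the two arms' rates side by side can show that the drug played a part, and nothing in section 12 puts them side by side.

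Prior local use does not settle this. Section 3 describes the group's own 51-patient comparison as retrospective and confounded, and other studies as retrospective or too small for outcomes. The trial is run because relative outcomes are unknown, so relative outcome safety is unknown too. At stake is whether a large excess in one arm during enrolment would meet any planned step able to show it.

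**Working it through.** **1. The plan's own figures.** Section 11: "we propose to enroll 200 lung transplant patients and 224 LVAD and heart transplant patients", and "212 patients will receive iEPO and 212 patients will receive iNO". 200 + 224 = 424, and 424/2 = 212 per arm, as stated. Enrolment runs "over a period of 24 to 36 months", so there are 24/3 = 8 to 36/3 = 12 quarterly reviews. At the midpoint of 30 months there are 30/3 = 10 quarters, hence nine looks before the end.

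**2. What each planned step can detect.**

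| Step | Acts on | Compares arms? |
|---|---|---|
| Listed drug effects (section 12) | named effects | not stated |
| PI sign-off and quarterly review (section 12) | relatedness of events | not stated |
| IRB reporting (section 12) | adverse events, policy not reproduced | not stated |
| Stopping criteria (section 4) | one subject's drug | no |
| Section 11 analysis | death and primary events | yes, at analysis |

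**3. What a by-arm look would add.** For n per arm and event rates p1 and p2, the chance of a flag at one look is the sum, over all pairs (x, y), of Bin(x; n, p1) × Bin(y; n, p2), counting only pairs whose two-sided Fisher exact p is below 0.001. The documents give no mortality rate, so those rates are assumptions. For PGD-3 the plan supplies both a rate ("Assuming the incidence rate of PGD-3 under iEPO treatment is 0.35") and a margin of 0.19, so the worse arm is set at 0.35 + 0.19 = 0.54. The upper limit printed in section 11 is 0.59, which does not follow from 0.35; the margin itself is used here.

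Single look half-way (212/2 = 106 per arm pooled; 100/2 = 50 lung; 112/2 = 56 heart transplant/LVAD):

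| Event and rates | n per arm | Flag at p<0.001 |
|---|---|---|
| Death 5% v 20%, pooled | 106 | 46% |
| Death 5% v 15%, pooled | 106 | 14% |
| Death 5% v 10%, pooled | 106 | 1.4% |
| Death 5% v 20%, lung only | 50 | 9% |
| Death 5% v 20%, heart/LVAD only | 56 | 12% |
| PGD-3 35% v 54%, lung | 50 | 5% |

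Nine equally spaced looks at pooled deaths before the end, p<0.001 at each, by simulation, taking each death as known at the next look:

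| Mortality | Flagged at some look |
|---|---|
| 5% v 20% | about 89% |
| 5% v 15% | about 48% |
| 5% v 10% | about 7% |
| 10% v 10% (false flag) | about 0.2% |

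**4. Reading.** Splitting deaths by population lowers the half-way figure from 46% to 9–12%, so the death flag should be pooled. Repeating the look each quarter matters more than any single look. The PGD-3 flag is weak for an excess equal to the margin. For scale, that excess is 100 × 0.19 = 19 cases in a fully enrolled lung arm and 50 × 0.19 = 9.5 at half enrolment.

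**The case against.** A reader might infer that an excess could not come to light until all 424 patients had been treated, or that monitoring would have prevented a definite number of deaths. The documents support neither. Section 11 says the populations are powered individually, so one could be analysed when it completes, although no such analysis is written. The IRB policy is not reproduced, and deaths or clusters may reach the IRB through it. The PI's review is not expressly confined to the listed effects. Subjects are unblinded at ICU discharge and the PI and statisticians hold the data, so informal detection is possible. Any count of avoided deaths would rest on assumed rates and on the flag always firing.

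It is also fair to say that threefold or fourfold mortality differences between two drugs in routine use are a favourable case for monitoring. At a doubling (5% v 10%) even nine looks flag only about 7%. The plan also gives a reason for light monitoring, and how much to do is partly a judgement.

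All of this limits the size of the point. The gap remains: no step compares these events between arms during enrolment, and relatedness judgements cannot do that job. Informal impressions gathered from unblinded subjects, with no threshold and no one assigned to act on them, are a poor substitute.

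**Conclusion.** The point holds in this form: section 12 plans no by-arm comparison of death, PGD-3, RVAD insertion or moderate/severe RV failure before the section 11 analysis, and its stopping rule acts on single subjects. The absence of a planned comparison is read from the text; the chance of detection by other routes cannot be determined from it.

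The gain from the remedy is protection against large excesses only. It rests on assumed mortality rates, on about nine pooled looks and on prompt recording of deaths. The change should be made because the data, the quarterly review and the statistician's access are already in place.

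**What to change.** In section 12, add to the quarterly review a by-arm table of deaths and of the primary failure event, listed by population: PGD-3 for lung transplant, RVAD insertion for heart transplant, moderate or severe RV failure for LVAD. A trial statistician who already has data access prepares it.

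Pre-specify a Haybittle-Peto flag, two-sided p<0.001, for deaths pooled across populations, and apply the same threshold to the primary failure event within each population. The statistician reports only flag or no flag. A flag is sent to the IRB for a decision on whether the trial continues.

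State in sections 12 and 13 that aggregate by-arm tables are withheld from the PI and treating investigators during enrolment. This has to be written out, because section 13 now gives the PI data access and section 4 unblinds subjects at ICU discharge. Withholding the tables does not stop someone assembling counts from unblinded subjects.

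Cost: one table a quarter from data already collected, and a short paragraph. One statistician sees by-arm counts during the trial. If each of the four flags behaved like the death flag, false flags would total at most about 4 × 0.2% = 0.8%, and so strict a threshold leaves the final error rate essentially unchanged.

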### 4. Design & Procedures:

#### Aim I – Development of a Definitive Clinical Trial Investigation.

**1. Randomization and Double-Blinding.** The clinical research unit (CRU) will receive preoperative notification of lung and heart transplantation patients by reviewing the transplant waitlist. Preoperative notification of LVAD implantation will be done by the review of the cardiothoracic surgical schedule. Using a 50% randomization process utilized and established by the CRU at Duke University Hospital, each eligible patient will be randomized to receive either iNO or iEPO. The primary endpoint data will be collected and documented in an electronic data capture system during the period of time the patient, clinical care team, and study team are blinded. Primary endpoint data collection will be complete prior to the subjects' discharge from the ICU, at which point the unblinding will occur. Since primary endpoint data collection will occur during the blinded period, the potential for bias will be substantially minimized.

**2. Measured Outcomes.** The primary endpoint for the comparison of efficacy in the Lung Transplant population will be the incidence of Grade 3 Primary Graft Dysfunction (PGD). This is defined by the International Society of Heart and Lung Transplantation (ISHLT) as severe hypoxemia with a PaO2-to-FiO2 ratio < 200 or the presence of venovenous extracorporeal membrane oxygenation (VV ECMO) at a time-point within the first 72

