### Subject Groups

Inhaled PVD therapy is administered to every patient undergoing thoracic transplantation and LVAD implantation at our institution and each patient is eligible for enrollment. Over a 3-year period (1 year for follow-up) we will prospectively enroll 200 lung transplant subjects and 224 heart transplant or LVAD implantation patients who will be informed and consented prior to their scheduled procedure. Potential subjects will be under the care of 1 or more investigators in this study. Consented subjects will be randomly assigned to 1 of 2 groups, iNO vs iEPO, to be initiated in the OR on the day of the operation based on accepted standard of practice and study protocol. Medication administration will be double-blinded, such that neither the surgical nor anesthesiology teams will be notified of the inhaled agent to which the patient has been randomized. Ability to unblind the delivery system will be made available to both teams if required to preserve optimal patient care. As per our standard practice, respiratory care services will manage the initiation and maintenance of inhaled PVDs in the OR and ICU, and these personnel will be the only practitioners notified of the actual delivered medication during study blinding.

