### Exclusion Criteria

- Combined Organ Transplantation (Heart-Lung, Heart-Liver, Heart-Kidney)
- Age < 18 years old
- Pregnancy (females of child bearing potential will receive pregnancy testing prior to cardiothoracic surgery as a standard of care)
- Known allergy to prostaglandin (rare)
- Refusal of blood products due to personal or religious preference.
- Subject is enrolled in another study protocol, which does not allow randomization of PVD therapy
- Heart transplant or durable LVAD recipients with adult congenital heart disease (CHD)
- Caveat: Does NOT meet exclusion criteria if the scheduled heart transplant or LVAD implantation is due to heart failure from a *previous heart transplantation* related to CHD, performed more than 90 days previous to the date of trial enrollment
- Patient is scheduled to undergo lung transplantation but has undergone heart transplantation in the previous 90 days
- Patient is scheduled to undergo durable LVAD implantation but has undergone heart transplantation in the previous 90 days
- Patient is scheduled to undergo heart transplantation but has undergone lung transplantation in the previous 90 days
- Patients with preoperative VV ECMO as a bridge to lung transplantation
- 

Stopping Criteria – In the event the following criteria are met and the clinical team is in agreement, subjects will be weaned off of their iPVD per institutional standard iPVD weaning practice. If adverse events are encountered, the drug will be immediately stopped without weaning.

- Venoaerterial (VA) ECMO insertion remains at end of operation
- VA ECMO insertion is performed postoperatively in the ICU
- LVEF < 30% on echocardiogram at the end of the operation for heart and lung transplant subjects

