## Research Summary – Inhaled Pulmonary Vasodilators in Thoracic Transplantation & LVAD Surgery

- LVEF < 30% for heart and lung transplant subjects on echocardiogram noted postoperative in the ICU
- Inhaled pulmonary vasodilation is halted for reasons other than standard weaning ordered by the clinical care team
- Adverse events related to the INO or EPO that affect the subject's welfare

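### Section 12 lists safety events by drug and counts rebound pulmonary hypertension only after weaning, so rebound after the protocol's own abrupt stops is not a pre-specified safety event

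*Combined protocol and SAP*

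**What the plan says.** Section 12 (Data & Safety Monitoring) bases the safety assessment on known rare effects, given drug by drug. The first list is "adverse effects of iNO (systemic hypotension, methemoglobinemia, and rebound pulmonary hypertension after appropriate weaning"; the second is "iEPO (systemic hypotension, non-surgical bleeding related to thrombocytopenia, flushing, and rebound pulmonary hypertension after appropriate weaning". On review it says "The PI will review and sign off on AE's as they occur and perform a quarterly review", and the PI decides whether each event is related to the study. No definitions, thresholds or time windows are given for the listed events.

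The Stopping Criteria in section 4 open by saying that patients who meet a criterion, with the clinical team's agreement, are weaned by institutional practice. They then add: "If adverse events are encountered, the drug will be immediately stopped without weaning". The criteria themselves include "Inhaled pulmonary vasodilation is halted for reasons other than standard weaning ordered by the clinical care team" and adverse events related to either drug.

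On blinding, section 4 (Aim I, Randomization and Double-Blinding) has primary endpoint data collected "during the period of time the patient, clinical care team, and study team are blinded", lasting until "discharge from the ICU, at which point the unblinding will occur". Under Subject Groups, respiratory care services manage the drug, and "these personnel will be the only practitioners notified of the actual delivered medication during study blinding".

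Under Data Collection, hemodynamic variables like those in Table 2 (which include systolic, diastolic and mean pulmonary artery pressure) and thrombocytopenia are recorded in all patients to 72 hours after initiation, whether or not the drug has stopped. After that, readings continue every 12 hours only while the drug continues.

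**The concern.** There are two problems of data capture.

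First, both lists attach the same condition to rebound: it must follow appropriate weaning. Yet the protocol provides for cessation without weaning, and an event on the section 12 lists, such as hypotension, can itself be what triggers it. Rebound after such a stop has no place in the stated safety events.

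Second, the lists differ by drug, and nothing says that both are checked in every patient. If site staff take the lists literally, some events will be sought in one arm and not in the other. In a trial meant to support iEPO as an acceptable alternative to iNO, a safety difference that reflects only where people looked would mislead in either direction. The plan also does not explain how a list keyed to the drug is used by a team that does not know the drug.

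**Working it through.** The plan gives no safety rate or safety sample size to reproduce. The only figure used from it is the arm size in section 11: 424 × 0.5 = 212.

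**Step 1. Count the events.**

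| Event | iNO list | iEPO list |
|---|---|---|
| Systemic hypotension | yes | yes |
| Rebound pulmonary hypertension, after weaning | yes | yes |
| Methemoglobinemia | yes | no |
| Non-surgical bleeding from thrombocytopenia | no | yes |
| Flushing | no | yes |

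There are five distinct events: two on both lists and 5 − 2 = 3 on one list only.

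**Step 2. Set the rebound condition against the ways the drug can stop.**

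| How the drug stops | Where stated | Rebound a listed event? |
|---|---|---|
| Protocol weaning | Data Collection | yes |
| Immediate stop for adverse events | Stopping Criteria | no |
| Halt other than standard weaning | Stopping Criteria | no |
| Switch to the other drug | section 11 | not stated |

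The condition is the same in both arms, so this gap does not by itself favour either drug.

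**Step 3. Check whether other data would show it.** From 2 hours to 72 hours the scheduled readings are at most 6 hours apart and do not depend on whether the drug is running. Rebound after a stop within 72 hours can therefore appear in the pulmonary pressures, although nothing labels it as a safety event. After 72 hours no reading is scheduled once the drug is off. This applies to weaned patients too, but for them rebound is at least a listed event.

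**Step 4. Check the stopping text against itself.** The lead-in to the Stopping Criteria says that patients meeting a criterion are weaned. Drug-related adverse events are one of the criteria. The next sentence says that adverse events mean no weaning, and it does not limit these to drug-related ones. The same event therefore falls under two routes, and the route decides whether later rebound counts under section 12.

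**Step 5. What one-arm ascertainment would do, if it happened.** Assume the same true rate q in both arms, with the event recorded in one arm of 212 only. The rates are assumptions, kept low because section 12 calls these effects rare. For k events against 0, the two-sided Fisher p is 2 × C(212,k)/C(424,k). This gives 0.061 at k = 5 and 0.030 at k = 6, so six events against none reach p < 0.05. The chance of this is P(X ≥ 6) with X binomial(212, q).

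| Assumed q | Expected events, 212 × q | Chance of p < 0.05 |
|---|---|---|
| 1% | 2.1 against 0 | 2% |
| 2% | 4.2 against 0 | 25% |
| 3% | 6.4 against 0 | 61% |

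The table shows the consequence of the literal reading. It is not evidence that the trial would be run that way.

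**The case against.** The strongest reply is that the parentheses in section 12 only describe what is known about each drug, and that all five events will be watched for in everyone. The text permits this reading, and nothing says that an event is sought only in patients given that drug. The PI's review of adverse events as they occur is not limited to the lists. Hypotension and post-weaning rebound are on both lists; thrombocytopenia, kidney injury and mortality are collected in all patients; and section 3 says that methemoglobin is read from arterial blood gases, though in the context of iNO. All of this stands. A reader might infer that safety cannot be compared between arms, and the documents do not support that.

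A reader might also infer that the PI must be unblinded to apply the lists. That does not follow. Relatedness is judged to the study and not to a named drug, a blinded PI can check all five events in every patient, and some quarterly reviews will come after unblinding at ICU discharge. What remains is that the protocol does not say how the lists are used during blinding.

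A third inference, that rebound after an abrupt stop will be missed altogether, fails on the 72-hour pressure schedule and the unrestricted adverse event review.

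Finally, the sponsor may have meant the weaning condition to separate a drug effect from the effect of sudden withdrawal. That is a fair aim, but recording how the drug was stopped achieves it without leaving events out of the definition.

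**Conclusion.** The point holds in a limited form. Rebound pulmonary hypertension after an immediate stop or another non-standard halt is outside the pre-specified safety events in both arms. Within 72 hours of initiation it may still be seen in the pressures; after that it depends on ad hoc reporting. The wording leaves open whether three of the five listed events are assessed in both arms, and it is silent on how drug-specific lists work under blinding.

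The number of patients stopped without weaning cannot be derived from the documents, so the extent of the rebound gap is unknown. Any distortion of the between-arm comparison depends on the literal reading being followed in practice and on assumed event rates; at 1% it would rarely reach significance. This is a cheap improvement to the plan and not a threat to the trial's main conclusions.

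**What to change.** In section 12 and on the adverse event form:

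- Replace the two lists with one list of all five events (systemic hypotension, methemoglobinemia, non-surgical bleeding from thrombocytopenia, flushing, rebound pulmonary hypertension), assessed identically in every patient without regard to arm.
- Count rebound after any cessation (weaned, abrupt or switched), and record the mode of cessation so that the groups can be reported separately.
- Tabulate all events by randomised arm.

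The Stopping Criteria in section 4 and the safety text in section 12 must also be reconciled on how adverse events, stopping and weaning relate. No change to the clinical stopping rule is proposed here.

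The cost is a sentence or two of protocol text, a revised form and a few more adverse event entries. Thrombocytopenia is already recorded in all patients, and methemoglobin is available wherever the blood gas analysis reports it.
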